9.5.1.3.2 VOLUMETRIC MRI

Volumetric MRI will be used to evaluate disease modification as indicated by measurements of brain atrophy, including the change from Baseline in terms of the measured hippocampal volume based upon the centralized measurement of the structure on repeated MRIs. A large number of studies, including the Alzheimer's Disease Neuroimaging Initiative, have shown that quantitative measurements of hippocampal, whole brain, and total ventricular volume provide robust and reliable biomarkers of disease progression, and potential for assessment of PD efficacy.

Volumetric MRI sequences will be collected for all subjects immediately following all safety MRI scans in the same imaging session. Volumetric MRI will be conducted at either 1.5T or 3T, and across multiple scanner types and the type of scanner used will be documented. Volumetric MRI analysis will be performed by a central imaging laboratory on MRI scans obtained at the times specified in [Table 6](#) and [Table 7](#), according to standard quality control and normalization procedures for measurements of the whole brain and total ventricular volume. Measurements of the right and left hippocampal volumes will be based on a validated algorithm and conducted in the same laboratory. Additional analysis of regions of interest and cortical thickness may also be performed.

Descriptions and detailed instructions for all imaging can be found in the imaging manual.

9.5.1.3.3 CEREBROSPINAL FLUID SAMPLING

CSF samples will be collected by LP (gravity drip method) at the timepoints specified in [Table 6](#) and [Table 7](#). The CSF sample taken at the Baseline Visit will only be performed after confirmation of an amyloid positive PET scan. See [Section 9.5.1.4.2](#) for further details.

9.5.1.4 Pharmacokinetic, Pharmacodynamic, Pharmacogenomic, and Other Biomarker Assessments

9.5.1.4.1 PHARMACOKINETIC ASSESSMENTS

Blood and CSF samples will be collected for the determination of the concentrations of E2609. Analyses of metabolite concentrations may be performed, depending on emerging data from other studies with E2609.

Samples from all subjects receiving active treatment will be analyzed. In addition, a predetermined percentage of placebo samples will be analyzed. Remaining placebo samples will be held in storage in the event that further confirmatory analysis is requested. Plasma concentrations of analytes will be quantified by liquid chromatography with tandem mass spectrometry methodology using a previously validated assay.

Blood samples will be collected as specified in [Table 6](#) and [Table 7](#). Two PK samples will be obtained: one at predose (trough) and another 1 to 6 hours postdose at Visits 5, 11, 14, and 16, and 4 to 8 hours postdose at Visit 7 and Visit 18 (or at the ED Visit). Therefore, subjects or their caregivers or informants must be instructed not to take their study drug at home on the day the PK sampling is performed. Instead, subjects will take the study drug with food at the clinic after collection of the predose PK sample. At Visit 7 and Visit 18 (or

at the ED Visit) the PK blood sample should be collected shortly before or shortly after completing the LP. (revised per Amendment 01) Although the PK sampling procedures at the ED visit should follow those of Visit 18, in the event that study drug has already been discontinued prior to the ED visit, then no dosing will be conducted. However, a PK sample at trough (before LP) will be collected, followed by LP at approximately the same time as previous visits. A second PK blood sample will be collected as close as possible in time to the LP, either shortly before or shortly after the LP. (revised per Amendment 01)

Blood will also be drawn where possible at the first report of an SAE or severe unexpected AE and at its resolution.

See the laboratory manual (to be supplied to study sites) for a description of the collection, handling, and shipping procedures for PK samples.

9.5.1.4.2 PHARMACODYNAMIC, PHARMACOGENOMIC, AND OTHER BIOMARKER, ASSESSMENTS

Biomarkers

Subjects will be encouraged to stay at the site after completion of LP for medical observation. At Baseline, a CSF sample will be collected by LP (gravity drip method) after fasting (preferred), or at least 2 hours after the most recent meal. The timing of the Baseline LP needs to be scheduled carefully such that subsequent LPs (Visit 7 and Visit 18) can be performed between 4 and 8 hours postdose and at a similar time of day (± 1 hour) for each individual subject. At visits where cognitive tests are also performed, if the tests are to be performed on the same day, the LP must be performed after the cognitive tests have been completed and the subjects should rest and drink some fluid to hydrate before the LP. (revised per Amendment 01) The CSF sample will not be taken at the ED Visit if this visit occurs within 3 months of a previous CSF sample. The CSF sample will be used for PD assessments including but not limited to CSF $A\beta(1-x)$, $A\beta(1-42)$, t-tau, p-tau, and BACE. The plasma sample will be used for $A\beta(1-x)$ analysis and may be used for exploratory biomarker analyses (eg, miRNA). $A\beta(1-x)$ in both CSF and plasma will be measured using a commercially based enzyme-linked immunosorbent assay (ELISA). The pre- and post-screening analysis of CSF $A\beta(1-42)$, t-tau, and p tau will be performed using ELISAs. BACE1 levels will be measured using internally developed fluorescence resonance energy transfer and ELISA based assay(s). Substrates of BACE1 inhibition may also be explored using Western blots or other amenable methodology if clinical observations warrant and if analytes can be reliably tested in samples collected.

The blood sample collected for PD analyses at Baseline should be collected on the same day shortly before or shortly after completing the LP at Baseline. The sample should be collected at fasting or at least 2 hours after the most recent meal. (revised per Amendment 01)

At the Baseline Visit, CSF and blood samples will be collected and stored for determination of prior exposure to any suspected infective agents in the event that the subject develops treatment-emergent AEs that warrant further investigation (eg, treatment-emergent infection). Testing may include, but not be limited to, serological tests, viral titer by quantitative polymerase chain reaction, or human leukocyte antigen genotyping.

Blood samples will be collected for PD assessments as specified in [Table 6](#) and [Table 7](#). See [Section 9.5.1.4.2](#) for further details.

For all subjects, baseline and on-study blood samples, DNA samples, and any collected CSF samples will be stored for up to 15 years.

See the laboratory manual (to be supplied to study sites) for a description of the collection, handling, and shipping procedures of the biomarker samples.

Pharmacogenomics

A blood sample will be obtained at Baseline and will be used to determine the *ApoE* genotype (homozygous or heterozygous E4 versus non-E4) and the *NAT2* phenotype of subjects enrolled in this study. The findings will be used in the statistical analysis to determine the effects on treatment response, safety, or PK of E2609. Details of which genotype / phenotype data will be applied to the analyses of efficacy, safety or PK will be discussed in the Statistical Analysis Plan.

The genomic DNA samples will be stored and may also be used to examine the role of genetic variability in subjects' absorption, distribution, metabolism, and excretion, the development of AEs, or underlying AD. Variations in E2609 exposure or the occurrence of AEs observed in the study population may be evaluated by correlation of single-nucleotide polymorphisms with PK, safety, or PD data.

Details of PGx testing may be provided and reported separately.

Amyloid PET

An amyloid PET scan will be performed at Screening to confirm deposition of amyloid in the brain. Longitudinal amyloid PET imaging will also be conducted after 18 months of treatment (or at ED, providing the subject has received at least 39 weeks of study drug). Longitudinal amyloid PET imaging will only be conducted until acceptable 18-month PET scans have been obtained for at least 25 subjects per treatment arm for each amyloid PET ligand used ([Table 6](#)). PET scanning will be performed with a locally approved A β imaging agent, eg, Amyvid. Descriptions and detailed instructions for all imaging can be found in the imaging manual.

Amyloid PET imaging is an exploratory measure of the potential disease-modifying effects of E2609.

Descriptions and detailed instructions for all imaging can be found in the imaging manual.

9.5.1.5 Safety Assessments

Safety assessments will consist of monitoring and recording all AEs and SAEs; regular monitoring of hematology, blood chemistry, lymphocyte subsets, Igs, and urine values; periodic measurement of vital signs and ECGs; performance of physical and neurological

examinations; centralized dermatological assessments; the C-SSRS; and safety MRIs as detailed in [Table 6](#) and [Table 7](#) will also be conducted. Peripheral blood mononuclear cells (PBMCs) will be collected at Baseline, during treatment, and posttreatment for exploratory immunomodulatory and immune-based analyses.

Every effort should be made to keep the site staff responsible for reviewing laboratory reports and assessing AEs separate from the site staff responsible for the efficacy assessments, particularly for the CDR (see [Section 9.4.6](#)). (revised per Amendment 01)

9.5.1.5.1 ADVERSE EVENTS AND EVENTS ASSOCIATED WITH SPECIAL SITUATIONS

An AE is any untoward medical occurrence in a subject or clinical investigation subject administered an investigational product. An AE does not necessarily have a causal relationship with the medicinal product. For this study, the study drug is E2609.

The criteria for identifying AEs in this study are:

- Any unfavorable and unintended sign (including an abnormal laboratory finding), symptom, or disease temporally associated with the use of an investigational product, whether or not considered related to the investigational product (Note: It is not necessary to report every sign or symptom as a separate AE if the overall disease [diagnosis] is being reported as an AE.)
- Any new disease or exacerbation of an existing disease
- Any deterioration in nonprotocol-required measurements of a laboratory value or other clinical test (eg, ECG or x-ray) that results in symptoms, a change in treatment, or discontinuation of study drug
- Recurrence of an intermittent medical condition (eg, headache) not present pretreatment (Baseline)
- An abnormal laboratory test result should be considered an AE if the identified laboratory abnormality leads to any type of intervention, discontinuation of study drug, or withholding of study drug, whether prescribed in the protocol or not

All AEs observed during the study will be reported on the eCRF. All AEs, regardless of relationship to study drug or procedure, should be collected beginning from the time the subject signs the study ICF through the last visit (Visit 20, as shown in [Table 7](#)). For subjects who discontinue early from study drug but undertake further efficacy assessments, AEs will only be collected for 3 months after the last dose of study drug, ie, through to the second follow-up visit (Visit 20). Subjects who fail screening primarily due to AE(s) must have the AE(s) leading to screen failure reported on the Screening Disposition eCRF. SAEs will be collected for 3 months after the last dose of study drug, ie, through to the second follow-up visit (Visit 20). For subjects who discontinue early from study drug but continue with further efficacy assessments, SAEs will be solicited only for 3 months after the last dose of study drug, i.e. up to the 2nd follow up visit (Visit 20). However, any SAEs volunteered by subjects after this time point must be reported according to standard procedures.

Abnormal laboratory values should not be listed as separate AEs if they are considered to be part of the clinical syndrome that is being reported as an AE. It is the responsibility of the investigator to review all laboratory findings in all subjects and determine if they constitute an AE. Medical and scientific judgment should be exercised in deciding whether an isolated laboratory abnormality should be classified as an AE. Any laboratory abnormality considered to constitute an AE should be reported on the Adverse Event eCRF.

Abnormal ECG (QTc) results, if not otherwise considered part of a clinical symptom that is being reported as an AE, should be considered an AE if the QTc interval is more than 450 ms and there is an increase of more than 60 ms from baseline. Any ECG abnormality that the investigator considers as an AE should be reported as such.

Cognitive decline will be assessed as a safety assessment in addition to an efficacy assessment. Cognitive assessments include the ADCOMS, ADAS-cog₁₄, MMSE, and CBB (see [Section 9.5.1.3.1](#)). If these assessments show cognitive decline during the Treatment Period, and if this cognitive decline is considered by the investigator to be excessive relative to the subject's recent AD history, this finding should be reported as an AE.

AEs that might indicate signals of possible drug abuse potential will require a more detailed follow-up through completion of a specific eCRF form. This includes AEs that fall into the following categories and examples of such AEs are provided in [Appendix 4](#).

- Euphoric mood
- Elevated mood
- Feeling abnormal
- Feeling drunk
- Feeling of relaxation
- Thinking abnormal
- Hallucination
- Inappropriate affect
- Mood disorders and disturbances
- Drug tolerance
- Psychosis
- Dissociative state

It is the responsibility of the investigator to review the results of the C-SSRS in all subjects and determine if any result constitutes an AE. Medical and scientific judgment should be exercised in deciding whether an isolated suicidality rating scale response should be classified as an AE (see [Section 9.5.1.5.11](#) for a description of the C-SSRS).

The following adverse events will require the collection of information sufficient to provide a detailed description of the event, treatment and outcome to the Medical Monitor for the study: any treatment-emergent significant laboratory abnormality; any seizures, herpes zoster infection, severe infection; any moderate to severe drug rash or any rash lasting more than

72 hours (regardless of severity); amyloid-related imaging abnormalities (vasogenic edema, macrohemorrhage, an area of superficial siderosis, or a new microhemorrhage); a “yes” answer to Type 4 or 5 suicidal ideation, or a “yes” response to any suicidal behavior on the C-SSRS.

All AEs must be followed through the second follow-up visit (Visit 20), or until resolution, whichever comes first. All SAEs must be followed to resolution or, if resolution is unlikely, to stabilization.

Every effort must be made by the investigator to categorize each AE according to its severity and its relationship to the study treatment.

Assessing Severity of Adverse Events

AEs will be graded on a 3-point scale (mild, moderate, severe) and reported in the detail indicated on the eCRF. The definitions are as follows:

| | |
|----------|--|
| Mild | Discomfort noticed, but no disruption of normal daily activity |
| Moderate | Discomfort sufficient to reduce or affect normal daily activity |
| Severe | Incapacitating, with inability to work or to perform normal daily activity |

The criteria for assessing severity are different than those used for seriousness (see [Section 9.5.1.5.2](#) for the definition of an SAE).

Assessing Relationship to Study Treatment

Items to be considered when assessing the relationship of an AE to the study treatment are:

- Temporal relationship of the onset of the event to the initiation of the study treatment
- The course of the event, especially the effect of discontinuation of study treatment or reintroduction of study treatment, as applicable
- Whether the event is known to be associated with the study treatment or with other similar treatments
- The presence of risk factors in the study subject known to increase the occurrence of the event
- The presence of nonstudy, treatment-related factors that are known to be associated with the occurrence of the event

Classification of Causality

The relationship of each AE to the study drug will be recorded on the eCRF in response to the following question:

Is there a reasonable possibility that the study drug caused the AE?

Yes (related) A causal relationship between the study drug and the AE is a reasonable possibility.

No (not related) A causal relationship between the study drug and the AE is not a reasonable possibility.

9.5.1.5.2 SERIOUS ADVERSE EVENTS AND EVENTS ASSOCIATED WITH SPECIAL SITUATIONS

An SAE is any untoward medical occurrence that at any dose:

- Results in death
- Is life-threatening (ie, the subject was at immediate risk of death from the AE as it occurred; this does not include an event that, had it occurred in a more severe form or was allowed to continue, might have caused death)
- Requires inpatient hospitalization or prolongation of existing hospitalization
- Results in persistent or significant disability/incapacity
- Is a congenital anomaly/birth defect (in the child of a subject who was exposed to the study drug)

Other important medical events that may not be immediately life-threatening or result in death or hospitalization but, when based on appropriate medical judgment, may jeopardize the subject or may require intervention to prevent one of the outcomes in the definition of SAE listed above should also be considered SAEs. Medical and scientific judgment should be exercised in deciding whether expedited reporting is appropriate in such situations.

For this study, the following events should always be considered serious and reportable using the criteria of important medical event if the event does not meet other serious criteria: new onset seizures, ocular herpes.

In addition to the above, events associated with special situations include pregnancy or exposure to study drug through breastfeeding; AEs associated with study drug overdose, misuse, abuse, or medication error. These events associated with special situations are to be captured using the SAE procedures but are to be considered as SAEs only if they meet one of the above criteria. All AEs associated with special situations are to be reported on the eCRF whether or not they meet the criteria for SAEs.

All SAEs must be followed to resolution or, if resolution is unlikely, to stabilization.

The following hospitalizations are not considered to be SAEs because there is no “AE” (ie, there is no untoward medical occurrence) associated with the hospitalization:

- Hospitalizations for respite care
- Planned hospitalizations required by the protocol
- Hospitalization planned before informed consent (where the condition requiring the hospitalization has not changed after study drug administration)

- Hospitalization for administration of study drug or insertion of access for administration of study drug
- Hospitalization for routine maintenance of a device (eg, battery replacement) that was in place before study entry

If possible, a blood sample for the measurement of study drug plasma concentration should be drawn at the first report of an SAE or a severe unexpected AE and at its resolution.

9.5.1.5.3 LABORATORY MEASUREMENTS

Clinical laboratory tests to be performed, including hematology, chemistry, urinalysis, and CSF are summarized in Table 4. Subjects should be in a seated or supine position during blood collection. Table 6 and Table 7 show the visits and time points at which blood for clinical laboratory tests and urine for urinalysis will be collected in the study.

See Section 9.3.3 for safety criteria for discontinuation from study drug related to absolute counts of CD4, CD8, and B lymphocytes, and for lymphocyte subset counts.

Table 4 Clinical Laboratory Tests

| Category | Parameters |
|-----------------------------|---|
| Hematology | Hematocrit, hemoglobin, platelets, red blood cell count, and white blood cell count with differential (bands, basophils, eosinophils, lymphocytes, monocytes, neutrophils), and (Screening and Baseline only), PT, PTT, and INR |
| Chemistry | |
| Electrolytes | Bicarbonate, calcium, chloride, phosphate, potassium, sodium |
| Liver function tests | Alanine aminotransferase, alkaline phosphatase, aspartate aminotransferase, gamma glutamyl transpeptidase, direct bilirubin, total bilirubin |
| Renal function tests | Blood urea/blood urea nitrogen, creatinine |
| Other | Albumin, cholesterol, globulin, glucose, lactate dehydrogenase, total protein, triglycerides, uric acid |
| Urinalysis | Bacteria, casts, crystals, epithelial cells, glucose, ketones, occult blood, pH, protein, red blood cells, specific gravity, white blood cells |
| Other | Lymphocyte subset analyses (see Table 5). Regulatory T cells will be measured using CD4, CD25, and CD127 cell surface markers and FoxP3 intracellular marker. PBMCs Ig analyses (IgG, IgA, and IgM). Viral screen (HCVAb [Hepatitis C] and HBsAg [Hepatitis B]). Viral characterization (including HSV1, HSV2 and CMV, etc) Serum pregnancy test (females of child bearing potential only) Tuberculosis Interferon Gamma Release Assays Tests for thyroid function (thyroid stimulating hormone, free triiodothyronine and free thyroxine) and vitamin B12 Blood sample for storage for subsequent testing of immune status Cerebrospinal fluid sampling |

CMV = cytomegalovirus, HBsAg = hepatitis B surface antigen, HCVAb = hepatitis C virus antibody, HSV = herpes simplex virus, Ig = immunoglobulin, INR = International Normalized Ratio, PBMC = peripheral blood mononuclear cell, PT = prothrombin time, PTT = partial thromboplastin time.

The 8 different surface markers (CD3, CD4, CD8, CD45, CD19, CD16, CD56, and CD14) and total lymphocyte counts will be measured in order to provide the lymphocyte subset data as shown in Table 5. In addition, Regulatory T cells will be measured using CD4, CD25, and CD127 cell surface markers and FoxP3 intracellular marker.

Table 5 Lymphocyte Subtyping

| Cell Type | Cell Surface Markers |
|----------------------|----------------------|
| T lymphocytes | CD3 |
| T helper cells | CD3+, CD4 |
| Cytotoxic T cells | CD3+, CD8 |
| Mature B cells | CD3-, CD19 |
| Natural killer cells | CD3-, CD16, CD56 |
| Macrophages | CD14 |

Clinical laboratory tests during all phases of the study will be performed by a central laboratory. All blood and urine samples will be collected and sent to the central laboratory on the day of collection unless otherwise instructed. In cases of a safety concern, blood samples will be split (or 2 samples drawn) to allow a local laboratory analysis in addition to the central laboratory. Laboratory certification as available will be included in the final clinical study report for this study.

A laboratory abnormality may meet the criteria to qualify as an AE as described in this protocol (see [Section 9.5.1.5.1](#) and the case report form [CRF] Completion Guidelines). In these instances, the AE corresponding to the laboratory abnormality will be recorded on the Adverse Event eCRF.

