9.4 Treatments

9.4.1 Treatments Administered

For this study the test drug is E2609 and the control drug is placebo. All study drugs are to be administered orally, QD, with food.

Treatments to be administered in Stage A and Stage B are shown below and in [Figure 1](#). The 2 highest E2609 doses (15 mg and 50 mg) taken into Stage B, after the PK/PD and safety review from Stage A, will be used for the mild to moderate AD population in Stage B. (revised per Amendment 01)

- Stage A: 3 doses (5 mg, 15 mg, and 50 mg) of E2609 or placebo
- Stage B, MCI/Prodromal Cohort: 3 doses (5 mg, 15 mg, and 50 mg) of E2609 or placebo
- Stage B, Mild to Moderate AD Cohort: 2 doses (15 mg and 50 mg) of E2609 or placebo. (revised per Amendment 01)

Study treatment will begin on Day 1 (at the study site) following Randomization and will continue for approximately 78 weeks. Please refer to [Table 7](#) and [Section 9.5.1.4.1](#) for specific information on drug administration on days when PK sampling is to be performed.

Study drug doses will remain the same for each individual subject unless the interim PK/PD analysis determines that an entire dose level requires adjustment ([Section 9.4.4](#)). See [Section 9.3.3](#) for safety-related discontinuation criteria of study drug. If a subject develops a concurrent illness during the treatment period, the investigator should discuss with the medical monitor on whether dosing with study drug needs to be temporarily suspended. As a general clinical guideline, dosing with study drug may be resumed after resolution or stabilization of the concurrent illness, after discussion with the medical monitor.

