- r: PET scanning will be performed with a locally approved amyloid β imaging agent, eg, Amyvid, if available or an agent under clinical investigation if no agents are approved locally; the imaging agent must remain unchanged for an individual subject throughout the study. A PET scan will only be performed at an ED Visit if the subject has been treated with study drug for at least 39 weeks.
- s: Site staff will contact the subject or the caregiver or informant the day before the PK blood sampling to provide instructions that subjects must not take their study drug at home on the day of the PK blood sampling. During this telephone contact with the subject or the caregiver or informant, the site staff should document the time that the subject took their study drug that day, ie, the day before the PK blood sampling.
- t: Two plasma PK samples will be obtained: one at predose (trough) and another 1 to 6 hours postdose at Visit 5, Visit 11, Visit 14 and Visit 16 and 4 to 8 hours postdose at Visit 7 and Visit 18 (or ED). Therefore, subjects or their caregivers or informants must be instructed not to take their study drug at home on the day the PK sampling is performed. Instead, subjects will take the study drug at the clinic after collection of the predose PK sample. At Visit 7 and Visit 18 (or ED) the PK blood sample should be collected shortly before or shortly after completing the LP. If at an ED Visit, the subject has already stopped study drug, then no dosing will take place, but the trough PK sample will still be collected, followed by LP at approximately the same time as at previous visits. A second PK blood sample will be collected as close as possible to the LP, either shortly before or shortly after the LP. (revised per Amendment 01)
- u: PD and exploratory biomarker blood samples should be collected at fasting or at least 2 hours after the most recent meal and, as far as is feasible, samples should be taken at the same time of day. At Visits 5, 11, 14, and 16 the PD blood samples should be collected predose.

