9.7.1.8.3 LABORATORY VALUES

Laboratory results will be summarized using International System of Units, as appropriate. For all quantitative parameters listed in [Section 9.5.1.5.3](#), the actual value and the change from baseline to each postbaseline visit and to the end of treatment (defined as the last on-treatment value) will be summarized by visit and treatment group using descriptive statistics. Qualitative parameters listed in [Section 9.5.1.5.3](#) will be summarized using frequencies (number and percentage of subjects), and changes from baseline to each postbaseline visit and to end of treatment will be reported using shift tables. Percentages will be based on the number of subjects with both nonmissing baseline and relevant postbaseline results.

Laboratory test results will be assigned a low/normal/high (LNH) classification according to whether the value was below (L), within (N), or above (H) the laboratory parameter's reference range. Within-treatment comparisons for each laboratory parameter will be based on 3-by-3 tables (shift tables) that compare the baseline LNH classification to the LNH classification at each postbaseline visit and at the end of treatment. Similar shift tables will also compare the baseline LNH classification to the LNH classification for the highest and lowest value during the treatment period.

[Appendix 1](#) (Sponsor's Grading for Laboratory Values) presents the criteria that will be used to identify subjects with treatment-emergent markedly abnormal laboratory values

(TEMAVs). Except for phosphate, a TEMAV is defined as a postbaseline value with an increase from baseline to a Grade of 2 or higher. For phosphate, a TEMAV was defined as a postbaseline value with an increase from baseline to a Grade of 3 or higher. When displaying the incidence of TEMAVs, each subject may be counted once in the laboratory parameter high and in the laboratory parameter low categories, as applicable.

Lymphocyte subsets (ie, CD4 [T helper cells], CD8 [cytotoxic T cells], CD19 [B cells], CD16/CD56 [natural killer cells] and CD14 [macrophages]) and regulatory T cells will be summarized in the same manner as other laboratory parameters. Mean lymphocyte subsets and the mean change from baseline in lymphocyte subsets will also be displayed graphically over time by dose.

Serum IgG, IgM, and IgA will be measured and summarized in the same manner as other laboratory parameters.

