| Calcium, serum-low (hypocalcemia) (conversion to mmol×0.25) | <8.5 – 8.0 mg/dL <2.13 – 2.0 mmol/L | <8.0 – 7.0 mg/dL <2.0 – 1.75 mmol/L | <7.0 – 6.0 mg/dL <1.75 – 1.5 mmol/L | <6.0 mg/dL <1.5 mmol/L |
| Calcium, serum-high (hypercalcemia) | >10.6 – 11.5 mg/dL >2.65 – 2.9 mmol/L | >11.5 – 12.5 mg/dL >2.9 – 3.1 mmol/L | >12.5 – 13.5 mg/dL >3.1 – 3.4 mmol/L | >13.5 mg/dL >3.4 mmol/L |
| Cholesterol, serum-high (hypercholesterolemia) (conversion to mmol/L ×0.02586) | 0 -19 years >169 – 300 mg/dL >4.37 – 7.75 mmol/L 19 -150 years >199 – 300 mg/dL >5.15 – 7.75 mmol/L | >300 – 400 mg/dL >7.75 – 10.34 mmol/L | >400 – 500 mg/dL >10.34 – 12.92 mmol/L | >500 mg/dL >12.92 mmol/L |
| Creatinine | Female >1.00 mg/dL – 1.5×1.00 Male >1.27 mg/dL – 1.5×1.27 | Female >1.5 – 3.0×1.00 Male >1.5 mg/dL – 3.0×1.27 | Female >3.0 – 6.0×1.00 Male >3.0 mg/dL – 6.0 ×1.27 | Female >6.0×1.00 Male >6.0×1.27 |
| Gamma glutamyl transpeptidase | Female >60 IU/L – 3.0×60 Male >65 IU/L – 3.0×65 | Female >3.0 – 5.0×60 Male >3.0 – 5.0×65 | Female >5.0 – 20.0×60 Male >5.0 – 20.0×65 | Female >20.0×60 Male >20.0×65 |
| Glucose, serum-high (hyperglycemia) (conversion to mmol/L ×0.0555) | Fasting glucose value >99 – 160 mg/dL >5.5 – 8.9 mmol/L | Fasting glucose value >160 – 250 mg/dL >8.9 – 13.9 mmol/L | >250 – 500 mg/dL; >13.9 – 27.8 mmol/L; hospitalization indicated | >500 mg/dL; >27.8 mmol/L; life-threatening consequences |
| Glucose, serum-low (hypoglycemia) | <65 – 55 mg/dL <3.6 – 3.0 mmol/L | <55 – 40 mg/dL <3.0 – 2.2 mmol/L | <40 – 30 mg/dL <2.2 – 1.7 mmol/L | <30 mg/dL <1.7 mmol/L life-threatening consequences; seizures |
| Phosphate, serum-low (hypophosphatemia) (conversion to mmol/L ×0.323) | not applicable | <2.5 – 2.0 mg/dL <0.8 – 0.6 mmol/L | <2.0 – 1.0 mg/dL <0.6 – 0.3 mmol/L | <1.0 mg/dL <0.3 mmol/L life-threatening consequences |
| Potassium, serum-high (hyperkalemia) | not applicable | >5.5 – 6.0 mmol/L | >6.0 – 7.0 mmol/L hospitalization indicated | >7.0 mmol/L life-threatening consequences |
| Potassium, serum-low (hypokalemia) | <3.5 mEq/L – 3.0 mmol/L | <LLN – 3.0 mmol/L; symptomatic; intervention indicated | <3.0 – 2.5 mmol/L hospitalization indicated | <2.5 mmol/L life-threatening consequences |
| Sodium, serum-high (hypernatremia) | >144 mEq/L – 150 mmol/L | >150 – 155 mmol/L | >155 – 160 mmol/L hospitalization indicated | >160 mmol/L life-threatening consequences |

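### High-glucose Grades 1 and 2 are fasting grades, but the protocol neither requires nor records fasting for the chemistry samples they grade

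*Protocol*

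**What the plan says.** Appendix 1 gives the high-glucose grades. Grade 1 is "Fasting glucose value >99 – 160 mg/dL >5.5 – 8.9 mmol/L" and Grade 2 is "Fasting glucose value >160 – 250 mg/dL >8.9 – 13.9 mmol/L". Grade 3 has no fasting label: ">250 – 500 mg/dL; >13.9 – 27.8 mmol/L; hospitalization indicated". Grade 4, above 500 mg/dL, has none either. Both copies of Appendix 1 in the file have the same glucose row.

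Section 9.7.1.8.3 uses these grades to find abnormal values. For every parameter except phosphate, "a TEMAV is defined as a postbaseline value with an increase from baseline to a Grade of 2 or higher".

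Glucose belongs to the chemistry panel in Table 4 (Section 9.5.1.5.3). The collection condition given there is posture: "Subjects should be in a seated or supine position during blood collection". The laboratory footnote to Table 6 and the chemistry row of Table 7 add no meal condition.

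Elsewhere the protocol does set one. Table 7, note u: "PD and exploratory biomarker blood samples should be collected at fasting or at least 2 hours after the most recent meal". Baseline PK blood and the CSF samples have a similar condition. On dosing, Section 9.4.1 says "All study drugs are to be administered orally, QD, with food", and placebo is one of the study drugs.

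**The concern.** The lowest grade that can make a hyperglycemia TEMAV is defined on a fasting value, but the samples to be graded come with no known meal state. Either fed values are graded against a fasting limit, or nobody can tell which values may be graded. The band affected runs from above 160 to 250 mg/dL. Above 250 mg/dL a value is Grade 3 or 4 whatever the meal state.

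What is at stake is how far one safety table can be trusted. If meals push values into that band, the hyperglycemia count rises in every arm and a real difference between arms becomes harder to see.

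**Working it through.** No figure in the plan needs reproducing, so the check sets the sections side by side and then illustrates the direction of the effect.

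**1. Grade limits.** Appendix 1 converts mg/dL to mmol/L with the factor 0.0555: 99 × 0.0555 = 5.495, 160 × 0.0555 = 8.88, 250 × 0.0555 = 13.875 and 500 × 0.0555 = 27.75. These match the printed 5.5, 8.9, 13.9 and 27.8. The limits are internally consistent, and the problem is the fasting label alone.

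**2. Meal state at each chemistry draw (Table 7, Section 9.5.1.4.1).**

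| Treatment visits with chemistry | PK/PD draw | What is known about meals |
|---|---|---|
| 5, 7, 11, 14, 16, 18 (six) | yes | Home dose withheld; dose and food given in the clinic after the predose PK sample; PD blood has a meal condition |
| 9, 15, 17 (three) | no | nothing |

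At the six PK/PD visits the meal condition belongs to the PD sample. It accepts blood taken two hours after eating, and no text ties the chemistry tube to the predose draw. So the chemistry sample is not required to be fasting at any of the nine visits.

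**3. Effect on the TEMAV count (assumed inputs).** Let *p* be a subject's true risk of a hyperglycemia TEMAV and *q* the chance of at least one purely meal-driven value in the band, independent of *p* and equal in all arms. Then:

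observed risk = 1 − (1 − *p*)(1 − *q*), and observed difference = (1 − *q*) × true difference.

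Take *p* = 5% on placebo and 15% on active, with 125 subjects per arm (500 ÷ 4). None of these risks comes from the documents. Power is for a two-sided 5% comparison of two proportions and is only a gauge of sensitivity, because no test is planned.

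| *q* | Placebo | Active | Difference | Ratio | Power |
|---|---|---|---|---|---|
| 0% | 5.0% | 15.0% | 10.0 points | 3.00 | 75% |
| 10% | 14.5% | 23.5% | 9.0 points | 1.62 | 44% |
| 20% | 24.0% | 32.0% | 8.0 points | 1.33 | 29% |
| 40% | 43.0% | 49.0% | 6.0 points | 1.14 | 16% |

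With no drug effect (5% in both arms) the observed difference is zero at every *q*.

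**4. Range for *q*.** If 1% to 5% of draws gave a meal-driven value and draws were independent, Visits 9, 15 and 17 alone would give 1 − (1 − 0.01)³ = 3.0% to 1 − (1 − 0.05)³ = 14.3%. All nine visits would give 1 − 0.99⁹ = 8.6% to 1 − 0.95⁹ = 37.0%. The per-draw figure is a pure assumption. Independence overstates the total, because the same subjects would tend to be high repeatedly, and using all nine visits ignores the partial protection at six of them.

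**The case against.** The strongest reply is that the protocol does not order fed samples to be graded. Appendix 1 is the criterion and contains the fasting label, so a non-fasting 170 mg/dL is, read literally, not Grade 2. That reading is fair, but it can only be applied if the fasting state is known, and the protocol does not ask for it. A laboratory requisition might carry such a field. The laboratory manual, however, is cited for PK and biomarker samples, and an analysis plan cannot restore a status that was never collected.

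Other replies stand and limit the point:

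- Grades 3 and 4 have no fasting label, so the mismatch does not cover the whole high-glucose scale.
- At six of the nine visits the home dose is withheld, which makes a fed sample less likely. For Visits 9, 15 and 17 no clock time for dosing is fixed, so it is an inference that subjects have already eaten.
- Laboratory summaries are descriptive, glucose is also reported as actual values, changes and shift tables, and no study-drug discontinuation criterion in Section 9.3.3 uses glucose.

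Two stronger readings are tempting. A reader might infer that the TEMAV count reflects meals instead of drug effect. The documents do not support this: placebo is also taken with food, arms are randomized and blinded, and each subject is compared with his or her own baseline. A reader might also infer that the rise from baseline is partly a move from a fasting to a fed state, because the Baseline CSF is preferably taken fasting. Baseline chemistry has no stated meal condition either, so this cannot be shown.

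**Conclusion.** The point holds in a narrow form. Grade 2, the entry level for a hyperglycemia TEMAV, is a fasting grade, and the protocol neither requires nor records fasting for the samples it grades. Meal-driven values above 160 mg/dL can enter the count in all arms. Provided meals affect all arms alike, which randomization and the common food instruction make reasonable, the absolute incidence is inflated and a true difference is shrunk by the factor 1 − *q*, with no false drug signal.

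The documents give no value for *q*, so the tables above show direction and not an estimate. In particular, 9% to 37% of subjects flagged without a drug effect should not be read as a finding. This is a minor point that affects one descriptive safety table and no decision rule.

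**What to change.** In Section 9.5.1.5.3, have fasting status or the time of the last meal recorded for each chemistry sample, Screening and Baseline included. In Section 9.7.1.8.3, add that the fasting-labelled glucose Grades 1 and 2 apply only to fasting samples, that Grades 3 and 4 apply to all samples, and that non-fasting glucose is summarized separately. The same line should say how a subject is handled whose baseline sample was not fasting, because a TEMAV is an increase from the baseline grade.

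The cost is one requisition field and a short addition to the TEMAV rule, with no change to dosing or visits. The downside is that fewer glucose values are graded at Grades 1 and 2, so the hyperglycemia count rests on fewer samples.
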